## 6.2. Sample size

Minimum and maximum sample size will significantly change according to the observed effect within the trial sample (expected **average** sample size is between 200 and 680 participants, figure 2). In particular, we expect to enroll 100 participants per arm at the first stage and then between 15 and 175 per arm for each eventual stage if the stopping rules were not met. The actual number of new participants in each arm will be calculated according to the maximum likelihood estimates on observed efficacy at each interim analysis with an overall conditional power for next stage equal to 90%. This approach allows either to minimize the number of enrolled participants if the experimental hypothesis is too conservative or to have a good power level if the experimental hypothesis is too optimistic. The average sample size with relative power and the overall probability for meeting stopping rules according to different level of efficacy of arm 1 vs. arm 2 are reported in figure 2 and figure 3, respectively.

	$H_0: \pi_T - \pi_C = 0$			
Critical values	Stage 1	Stage 2	Stage 3	
Reject H0 (Efficacy)	3.421	2.419	1.975	1.975
Accept H0 (Futility)	-0.695	1.002	1.975	1.975
Information rate	0.333	0.667	1	1
alpha spent	0.0003	0.0079	0.025	0.025

*Table 1 Preplanned critical values (Fisher test) for application of early stopping rules*

**K = 3; alpha = 0.025, one-sided, binding futility = (-0.695, 1.002), Delta = 0 (O'Brien and Fleming design).**

Figure 1 Plot for application of early stopping rule. Uncertainty area (i.e.  $H_0$  is neither accepted nor rejected) lies above the green line and below the red lines

### 6.3. Analysis of efficacy (primary outcome)

Interim analyses and final analysis will be carried out by taking into account the potential effect of each individual component of the adaptive design. The interim analyses will provide:

- a) estimate of efficacy as risk difference and relative 95% CI
- b) criteria for stopping rules
- c) if the stopping rules are not met the analysis will provide the number of participants to be randomized for the subsequent stage in each arm.
- d) final analysis will provide efficacy as difference estimate of efficacy as risk difference and relative 95% CI

Subgroup analyses will be carried out if the sample size will allow to. In this case, the following groups will be taken into consideration:

- a) Patients requiring only oxygen therapy, either low-flow or high-flow (HFNC) during the study period
- b) Patients requiring only low-flow oxygen therapy during the study period;

- c) Patients requiring high-flow oxygen therapy (HFNC) but not ventilatory support during the study period
- d) Patients requiring mechanical ventilation, either invasive or noninvasive during the study period
- e) Patients requiring noninvasive mechanical ventilation but not invasive mechanical ventilation during the study period
- f) Patients requiring invasive mechanical ventilation during the study period.

All the analyses will be conducted by the trial statisticians following the intention-to-treat principle.

In case of deviations from the study protocol, such as cross-over between arms, sensitivity analysis will be carried out (eg., *per protocol* analysis).

[figure not shown]

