### 4.2. Eligibility Criteria

Inclusion criteria are the following:

- a) Able to understand and sign the informed consent form
- b) SARS-CoV-2 positive on at least one upper respiratory swab or bronchoalveolar lavage
- c)  $\text{PaO}_2 \leq 60$  mmHg or  $\text{SpO}_2 \leq 90\%$  or on HFNC, CPAP or NPPV at randomization
- d) Age  $\geq 18$  years old at randomization

Exclusion criteria are the following:

- a) On invasive mechanical ventilation (either intubated or tracheostomized)
- b) Heart failure as the main cause of acute respiratory failure
- c) On long-term oxygen or home mechanical ventilation
- d) Decompensated liver cirrhosis
- e) Immunosuppression (i.e., cancer on treatment, post-organ transplantation, HIV-positive, on immunosuppressant therapy)
- f) On chronic steroid therapy or other immunomodulant therapy (e.g., azathioprine, methotrexate, mycophenolate, convalescent/hyperimmune plasma)
- g) Chronic renal failure with dialysis dependence
- h) Progressive neuro-muscular disorders
- i) Cognitively impaired, dementia or decompensated psychiatric disorder
- j) Quadriplegia/Hemiplegia or quadriparesis/hemiparesis
- k) Do-not-resuscitate order

- l) Participating in other clinical trial including experimental compound with proved or expected activity against SARS-CoV-2 infection
- m) Any other condition that in the opinion of the investigator may significantly impact with patient's capability to comply with protocol intervention
- n) Refuse to participate in the study or absence of signed informed consent form.

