#### 4.6. Schedule of assessments

Time-line	Activity/Treatment	Measurements
Day 1	Consent obtained; randomization; study drug administration by randomized group; vital signs monitoring.	SpO 2 (%), PaO 2 (mmHg), CRP (mg/L), PaO 2 /FiO 2 (mmHg)*, baseline data collection §
Day 3	Treatment continued, as defined above	CRP (mg/L), Worst daily PaO 2 /FiO 2 (mmHg)*, WHO clinical progression score
Day 7	Treatment continued, as defined above	CRP (mg/L), Worst daily PaO 2 /FiO 2 (mmHg)*, WHO clinical progression score

Day 14	Treatment continued, as defined above	CRP (mg/L), Worst daily PaO 2 /FiO 2 (mmHg)*, WHO clinical progression score
Day 28		Patient's outcome determined (mortality, total days of mechanical ventilation, days of invasive mechanical ventilation, days of noninvasive mechanical ventilation) and final data collection °
Hospital discharge		Patient's outcome determined (mortality, days of hospitalization)

\* The type of respiratory support (low-flow oxygen therapy, HFNC, NPPV, IMV, ECMO) under which the PaO2/FiO2 is obtained must be always specified in the appropriate section of the data collection form.

[figure not shown]
§ Baseline data should include:

- a) Date of birth
- b) Sex
- c) BMI
- d) Smoke (yes/no/former)
- e) Date of the onset of symptoms
- f) Date of hospitalization
- g) Date of randomization
- h) Type of respiratory support at randomization (i.e., low-flow oxygen, HFNC, NPPV)
- i) Comorbidities (COPD, Bronchiectasis, Asthma, Other respiratory disease, Pre-existing Diabetes, Atrial fibrillation, Coronaropathy, Chronic heart failure, Other relevant disease of the heart and large vessels, Pulmonary embolism/chronic thromboembolism, Other conditions requiring long-term anticoagulation, Systemic hypertension, Autoimmune Disease, OSA/OHS, Chronic Kidney Disease, Minor stroke, History of Cancer)

°Other data to be collected:

- a) Date of treatment initiation
- b) Date of full-dose treatment completion
- c) Date of de-escalation completion
- d) Deviation from protocol (yes/no; if yes, date of deviation and reason for deviation)
- e) Remdesivir (yes/no)
- f) Anticoagulation:
  - LMWH (prophylactic/anticoagulant)
  - Unfractionated heparin
  - Warfarin

- NOAC

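### All six subgroups for the primary outcome are defined by respiratory support over the study period, so none is fully fixed at randomisation and survival comparisons within them can be biased

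*Protocol*

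**What the plan says.** Protocol section 6.3, on the primary outcome, makes subgroup analyses conditional on sample size and names six groups. Group a) is "Patients requiring only oxygen therapy, either low-flow or high-flow (HFNC) during the study period". Groups b) and c) divide it into those who stay on low-flow oxygen alone and those who need HFNC without going on to ventilation. Group d) takes everyone who is ventilated by either route. Group e) is the part of d) that is never ventilated invasively, and group f) is "Patients requiring invasive mechanical ventilation during the study period". Each of the six is worded by support over that same period, and none by support at entry.

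The groups overlap: a) contains b) and c), and d) contains e) and f). The same section states that all analyses follow intention to treat.

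Other sections bear on this:

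- Section 4.2 excludes patients who are "On invasive mechanical ventilation (either intubated or tracheostomized" but admits patients on HFNC, CPAP or NPPV.
- Section 2.2 makes less need for, and shorter, mechanical ventilation secondary objective (a). Section 4.5 makes ventilation-free days a secondary outcome.
- Section 4.4 escalates support when the previous line has failed to improve oxygenation after 24 to 48 hours. Section 5.1 states that the trial is open label.
- Section 4.6 collects at baseline "Type of respiratory support at randomization (i.e., low-flow oxygen, HFNC, NPPV". Section 6.3 does not use this item.

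**The concern.** A subgroup comparison inherits the protection of randomisation only if membership is settled before treatment can act on it. Here the grouping variable is partly an outcome, and one the experimental treatment is intended to change. If methylprednisolone keeps some patients off a ventilator, those patients sit in one subgroup in the methylprednisolone arm, while their counterparts sit in another in the dexamethasone arm. The two arms within a subgroup then differ in prognosis even if the drug alters nobody's survival. Because clinicians know the arm when they escalate, membership may also reflect that knowledge.

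At stake is the question of who benefits. The rationale in section 2.1 cites a large UK trial in which steroid benefit differed by respiratory support, so readers will look to these subgroups. They are the only ones section 6.3 lists, and as defined they cannot answer the question reliably.

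**Working it through.** **1. When is membership settled?**

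| Subgroup | Known at randomisation? |
|---|---|
| a), b), c), e) | No. Each requires that no later escalation beyond the stated level occurred. |
| d) | In part. A patient on NPPV at entry belongs from the start; others join when ventilated later. |
| f) | No. Invasive ventilation at entry is an exclusion, so every member arises afterwards. |

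No subgroup is fully determined at baseline.

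**2. What size could the bias have?** The protocol gives no figure for the subgroups and no ventilation rates by arm. One input comes from it: 77% control survival (section 6.1), that is 23 deaths per 100. The rest are assumptions:

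- 25 of 100 controls are intubated, with 15 deaths. The other 75 have 8 deaths (15 + 8 = 23).
- Methylprednisolone spares intubation in k of the 25, whose mortality m is 30% with or without intubation.
- Treatment changes no patient's death, so the methylprednisolone arm also has 23 expected deaths per 100.

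Expected mortality on methylprednisolone is (15 − km)/(25 − k) if intubated and (8 + km)/(75 + k) if not. Controls have 15/25 = 60% and 8/75 = 10.7%.

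| k spared | Intubated, MP vs DM | False gap | Not intubated, MP vs DM | False gap |
|---|---|---|---|---|
| 2 | 14.4/23 = 62.6% vs 60% | 2.6 points | 8.6/77 = 11.2% vs 10.7% | 0.5 points |
| 5 | 13.5/20 = 67.5% vs 60% | 7.5 points | 9.5/80 = 11.9% vs 10.7% | 1.2 points |
| 10 | 12/15 = 80% vs 60% | 20 points | 11/85 = 12.9% vs 10.7% | 2.3 points |

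In every row methylprednisolone looks harmful in both subgroups, although it harms no one.

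**3. Which direction?** The gaps simplify to k(0.60 − m)/(25 − k) for the intubated and k(m − 8/75)/(75 + k) for the others. The intubated subgroup shows false harm if the spared patients have mortality below 60%, and false benefit if above. The non-intubated subgroup shows false harm if they have mortality above 10.7%, and false benefit if below. The sign therefore depends on who is spared, which the protocol cannot tell us.

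**4. Could such gaps reach nominal significance?** A second model was simulated with 340 per arm (half of 680, the upper end of the expected average sample size), 23% mortality in both arms and two-sided 5% tests. As assumptions, 50% of patients need oxygen only on either drug (5% mortality), 10% need ventilation on dexamethasone but not on methylprednisolone (20%), and 40% need it on both (46.2%).

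- Oxygen-only mortality: MP (0.50 × 5% + 0.10 × 20%)/0.60 = 7.5%; DM 5.0%.
- Ventilated mortality: MP 46.2%; DM (0.10 × 20% + 0.40 × 46.2%)/0.50 = 41.0%.
- False-positive rates were 15% and 16%, and 29% for at least one of the two.

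The table varies the share spared, with mortality among the spared between 15% and 30%:

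| Share spared ventilation | Oxygen-only, false-positive rate | Ventilated, false-positive rate |
|---|---|---|
| None (membership independent of treatment) | about 5% | about 5% |
| 5% | 7–14% | 5–8% |
| 10% | 10–33% | 8–21% |
| 15% | 14–55% | 12–47% |

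The whole-trial comparison stayed at 5% throughout.

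**The case against.** The strongest case on the other side concerns weight. The subgroups are optional. They carry no alpha, feed no stopping rule and do not enter the sample-size recalculation, and section 6.3 attaches no hypothesis or named test to them. All of that stands. A reader might infer that the trial's main conclusion is at risk, but nothing in the protocol supports that: the primary comparison uses all randomised patients.

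A reader might also take the 20-point gap as the expected error. It is the steepest row of an assumed scenario, with 10 of 25 intubations avoided. With 2 avoided the gap is 2.6 points.

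Nor is it right to say that membership always arises after randomisation. That is wholly true of f), but a patient on NPPV at entry is in d) from the start. The core survives, because d) pools such patients with those ventilated later.

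Two possible defences do not succeed. Intention to treat keeps patients in their assigned arm but does not make the arms comparable within a group selected afterwards. Running the subgroups only with enough patients makes a biased estimate more precise, not less biased.

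**Conclusion.** The point holds, as a defect in stated definitions rather than detail left for an analysis plan. Survival comparisons within a) to f) can be biased whenever treatment changes who is escalated, which is what secondary objective (a) hopes for. They would be free of this bias if escalation were unaffected by arm.

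Under the assumptions above, the false excess mortality is about 2.6 to 20 points in the intubated subgroup and about 0.5 to 2.3 points in the non-intubated subgroup. These figures show mechanism and possible size; they are not predictions. A reader might infer from them that the bias always runs against methylprednisolone. It need not, since the sign depends on the prognosis of those spared.

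The primary analysis, alpha and power are untouched and the subgroups are conditional, so this is a should-fix.

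**What to change.** In section 6.3, replace a) to f) with subgroups by type of respiratory support at randomisation, using the categories already collected under section 4.6: low-flow oxygen, HFNC and NPPV. State that CPAP at entry is counted with NPPV, because section 4.2 admits patients on CPAP but the baseline item does not name it. Preferably, assess these subgroups by a treatment-by-subgroup interaction; that detail may sit in the SAP.

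If results by support received during the study are still wanted, label them descriptive and draw no between-arm inference from them.

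The cost is a change of wording and giving up inferential claims by support received. No new data item or additional patients are needed. The change is best made before the first unblinded interim analysis, so that it cannot appear data-driven.

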#### 6.4. Analysis of secondary outcomes

Binary variables (i.e., proportion of patients requiring tracheostomy) will be modelled according to separate logistic regression models to assess the potential effect of each different treatment arm. All models will be adjusted for the effect of age and gender in the case of unbalanced groups following randomization.

[figure not shown]
Continuous variables including the number of days free from mechanical ventilation, number of days of hospitalization, C-reactive protein level (mg/L) at study day 3, 7, 14 and PaO2/FiO2 ratio (mmHg) at study day 3, 7 and 14 after randomization will be modelled by linear regression models and the estimates will be given adjusted for age and sex in the case of unbalanced groups following randomization.

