## 2.2. Objectives

We hypothesize that in patients hospitalized for COVID-19 pneumonia requiring respiratory support (either oxygen supplementation, HFNC, NPPV), the methylprednisolone protocol is superior to the dexamethasone protocol in improving clinical outcomes.

The primary objective is to assess the efficacy of the methylprednisolone protocol in improving survival by day 28 compared to the dexamethasone protocol.

The secondary objectives are to compare efficacy of the two protocols in achieving:

- a) Reduction in the need and duration of mechanical ventilation
- b) Reduction in hospital mortality
- c) Reduction in the duration of hospitalization
- d) Reduction in duration of requirement for oxygen supplementation

Additional end-points include anti-inflammatory potency based on longitudinal reduction in systemic C-reactive protein levels and reduction in disease progression based on the WHO clinical progression scale.(9)

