##### Secondary outcome measures

- Number of days free from mechanical ventilation (either NPPV or IMV) by study day 28 in both arms
- Number of days of hospitalization among survivors in both arms
- Proportion of patients requiring tracheostomy in both arms
- C-reactive protein level (mg/L) at study day 3, 7 and 14 in both arms
- PaO2/FiO2 ratio (mmHg) at study day 3, 7 and 14 in both arms
- WHO clinical progression scale at study day 3, 7 and 14 in both arms(9)

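### Section 6.4 models C-reactive protein and PaO2/FiO2 levels at days 3, 7 and 14 without the day-1 value and gives no overall longitudinal contrast, although 2.2 names a longitudinal reduction in CRP

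*Protocol*

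**What the plan says.** Section 2.2 of the protocol states: "Additional end-points include anti-inflammatory potency based on longitudinal reduction in systemic C-reactive protein levels". The outcome list in section 4.5 turns this into "C-reactive protein level (mg/L) at study day 3, 7 and 14 in both arms" and lists PaO2/FiO2 on the same three days.

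The schedule in section 4.6 has both CRP and PaO2/FiO2 measured on day 1 and again on days 3, 7 and 14.

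Section 6.4 groups the day-specific levels with ventilation-free days and hospital days as continuous variables. All of these "will be modelled by linear regression models and the estimates will be given adjusted for age and sex", and the adjustment is made only "in the case of unbalanced groups following randomization". The section names no day-1 value, no time term, no repeated-measures structure, no main day and no summary over days. For the binary outcomes it speaks of "will be modelled according to separate logistic regression models"; it does not use the word separate for the linear models.

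**The concern.** The objective describes a course over time, while the analysis takes levels on three days. In section 6.4 each day's level sits in the same list as outcomes that have one value per patient, all under one generic linear regression. The most natural reading is therefore one fit per day. The alternative, pooling the days in an ordinary regression, would ignore the correlation between readings from the same patient.

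Two things are at stake. First, the day-1 reading, usually among the strongest predictors of a later reading of the same marker, is collected but enters no stated model. Age and sex are the only covariates named, and they are conditional on imbalance. Secondly, the reader gets up to three CRP contrasts and no estimate that sums up the longitudinal effect on which section 2.2 rests its statement about anti-inflammatory potency.

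For PaO2/FiO2 only the first point applies, since section 2.2 sets no longitudinal objective for it.

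**Working it through.** The protocol gives no standard deviation, effect size, correlation or test level for CRP or PaO2/FiO2. There is thus no planned figure to reproduce, and the correlations below are assumptions shown as a range.

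**1. Do the daily level contrasts bear on reduction?** Let Y1 be the day-1 value and Yt the value on day t. The arm difference in mean change is

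[E(Yt | MP) − E(Y1 | MP)] − [E(Yt | DM) − E(Y1 | DM)].

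Randomisation makes E(Y1 | MP) = E(Y1 | DM), so this equals E(Yt | MP) − E(Yt | DM). With complete data, the planned contrast on each day has the same expectation as the arm difference in reduction from day 1 to that day. The plan does not give the reduction within an arm, a trajectory, or one overall effect.

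**2. What does omitting the day-1 value cost?** Let ρ be the correlation between the day-1 and day-t readings (after age and sex, if those are in the model), with equal variances. Relative to a follow-up-only comparison, the variance of the arm difference with day-1 adjustment is 1 − ρ². The standard error without adjustment is larger by the factor 1/√(1 − ρ²).

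| Assumed ρ | Adjusted variance, 1 − ρ² | Variance saved | SE inflation if omitted |
|---|---|---|---|
| 0.3 | 0.91 | 9% | 1/0.954 = 1.048, about 5% |
| 0.5 | 0.75 | 25% | 1/0.866 = 1.155, about 15% |
| 0.7 | 0.51 | 49% | 1/0.714 = 1.400, about 40% |

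An unadjusted change score would not be a safe substitute. Its relative variance is 2(1 − ρ), that is 1.4, 1.0 and 0.6 at the same three values. It is worse than the plain level at 0.3, no better at 0.5, and worse than covariate adjustment at all three.

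**3. What does a joint model add?** With complete data, a repeated-measures model with unstructured covariance and day-specific covariate effects returns the same daily contrasts as day-by-day regressions with the same covariates. For the daily contrasts the gain in step 2 therefore comes from the day-1 value and not from linking the days. The joint model contributes in two other ways:

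- It supplies an overall contrast with a correct standard error.
- It handles incomplete data better. A day-by-day fit uses only patients with a reading that day, so the three contrasts may describe three different sets of patients. The joint model keeps everyone with at least one follow-up reading and conditions on earlier readings.

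**The case against.** The strongest reply is that repeated-measures structure, baseline terms and the main contrast are commonly left to a statistical analysis plan, which is not shown. Separate daily fits are also inferred, not stated. Both remarks are fair. But section 6.4 is not silent: it fixes a model type and names the covariates, and as written the day-1 value is not among them. That much stands on any reading.

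Several stronger conclusions are tempting, and the protocol does not support them.

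- **A reader might infer that the reduction is never estimated.** Step 1 shows otherwise for the arm difference, missing data aside.
- **A reader might infer a large fixed gain from averaging the three days.** With equal correlation throughout and day-1 adjustment, the relative variance of the three-day mean is (1 + 2ρ)/3 − ρ², or 0.443, 0.417 and 0.310 at 0.3, 0.5 and 0.7. But this is a different estimand, and the gain in power assumes the same effect on every day. It also depends on the correlation pattern. Under autoregressive correlation of 0.7 between successive visits, the adjusted mean has variance 0.492 against 0.510 for day 3 alone, only 3.5% lower. The protocol also gives no inputs from which to calculate power for CRP.
- **A reader might infer an inflated false-positive rate for the potency statement.** If any one of three tests at an assumed two-sided 5% counted as success, the chance of at least one false positive would be 13.6%, 12.5% or 10.9% at between-visit correlations of 0.3, 0.5 or 0.7. The protocol states no such success rule and no test level for CRP. Its one-sided 0.025 belongs to the primary outcome alone.

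A further objection concerns the remedy: making the three-day average the only result would demote outcomes that section 4.5 prespecifies, and a mixed model does not settle readings truncated by death. This stands. The planning survival of 77% and 87% in section 6.1 implies 23% and 13% mortality by day 28, so truncation is not negligible.

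**Conclusion.** The point holds as a minor improvement. Sections 2.2, 4.5 and 6.4 do not line up on CRP, and section 6.4 leaves unused a day-1 value that section 4.6 already collects. The daily contrasts are valid with complete data but imprecise: the standard error is about 5% larger than it need be at an assumed baseline correlation of 0.3, 15% at 0.5 and 40% at 0.7. The loss is small at the low end and material from 0.5 upwards. The same arithmetic applies to PaO2/FiO2, although section 4.6 specifies the worst daily value from day 3 but not for day 1, which could lower the correlation.

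The figures rest on the assumed correlations, equal variances and complete readings. No overall longitudinal effect is estimated, and that follows from the text without any assumption. The primary outcome and its error control are unaffected.

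**What to change.** In section 6.4, for each of CRP and PaO2/FiO2, replace the generic linear regression by one linear mixed model for repeated measures over days 3, 7 and 14. It should contain:

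- arm, day and arm-by-day;
- the day-1 value and its interaction with day, prespecified and included whatever the balance between groups;
- an unstructured within-patient covariance.

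Report the day 3, 7 and 14 contrasts from this model, so that the outcomes listed in section 4.5 are kept. Add one prespecified overall arm contrast, which for CRP is the estimate that answers section 2.2. The mean of the three daily contrasts is one candidate: with day-1 adjustment it estimates the average arm difference in change from day 1. Align the wording of sections 2.2 and 4.5 with the choice.

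The cost is wording and a standard procedure in Stata, the software named in section 6.5 for secondary outcomes. No new data are needed. There are two drawbacks. An effect confined to one day is diluted in the overall contrast, which is why the daily contrasts stay. Readings missing after discharge or death are handled under a missing-at-random assumption, so a sensitivity analysis for truncation by death should be specified with the model.

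### Section 6.4 adjusts the secondary models for age and sex only if the groups look unbalanced, and does not name the day-1 CRP and PaO2/FiO2 values that the trial collects as covariates

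*Protocol*

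**What the plan says.** Protocol 6.4 states the adjustment rule twice. For binary outcomes, with tracheostomy as the example, logistic regression is used and "All models will be adjusted for the effect of age and gender in the case of unbalanced groups following randomization". For ventilation-free days, days of hospitalization, CRP and PaO2/FiO2, linear regression is used and "the estimates will be given adjusted for age and sex in the case of unbalanced groups following randomization". Age and sex are the only covariates named. The section does not say which variable must be unbalanced, by what measure, by how much, or who decides.

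Protocol 4.5 defines the CRP outcome as "C-reactive protein level (mg/L) at study day 3, 7 and 14 in both arms", and PaO2/FiO2 at the same days. Protocol 4.6 schedules both on day 1, alongside the baseline data collection. Protocol 2.2 describes an additional end-point of "anti-inflammatory potency based on longitudinal reduction in systemic C-reactive protein levels".

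For context, the trial is open label with block randomization and no stratification factor named (5.1). Secondary outcomes are analysed at the end of the trial (6.5).

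**The concern.** There are two weaknesses in one rule.

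**Chance imbalance is the wrong trigger.** A covariate belongs in the model because it predicts the outcome, and that can be decided in advance. With an undefined trigger, the model is settled only once the data are in. For a logistic model this changes more than precision. The odds ratio adjusted for prognostic covariates and the unadjusted odds ratio are different quantities even under perfect balance. The reader of the protocol therefore cannot tell which one will be reported for tracheostomy.

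**The most useful covariate is not named.** For CRP and PaO2/FiO2, the patient's own day-1 value is likely to be a strong predictor of later values. Leaving it out gives up precision and leaves any chance day-1 difference between the arms in the estimate. The stated trigger does not help, because at most it brings in age and sex. For CRP, the raw-level model also fits poorly with an end-point described in 2.2 as a reduction over time.

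**Working it through.** The protocol gives no precision or power figure for the secondary models, so there is no stated number to reproduce here. Its design figures concern the primary outcome. Recomputing the boundaries in Table 1 with binding futility gives cumulative alpha of 0.0003, 0.0079 and 0.0250, which matches the table. Nothing below touches it.

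**1. Precision lost for CRP and PaO2/FiO2**

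Input: r, the correlation between the day-1 value and the follow-up value. The documents give none, so a range is assumed.

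Formulas:
- Variance ratio, adjusted to unadjusted: 1 − r².
- Equivalent gain in patients: 1/(1 − r²) − 1.
- Power, for a comparison with 80% power unadjusted (assumed, two-sided 5%): Φ[(1.96 + 0.84)/√(1 − r²) − 1.96].

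| r (assumed) | Variance ratio | Fall in standard error | Equivalent extra patients | Power, from 80% |
|---|---|---|---|---|
| 0.3 | 0.91 | 5% | 10% | 84% |
| 0.5 | 0.75 | 13% | 33% | 90% |
| 0.7 | 0.51 | 29% | 96% | 98% |

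**2. Chance baseline difference left in the estimate**

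Inputs from 6.2: 100 per arm if the trial stops at stage 1, and at most 100 + 175 + 175 = 450 per arm. In SD units, the standard error of a difference in means is √(2/n).
- n = 100: √(2/100) = 0.141. A day-1 gap beyond 1.96 × 0.141 = 0.28 SD arises by chance in 5% of trials. At r = 0.5 it carries 0.5 × 0.28 = 0.14 SD into the unadjusted estimate.
- n = 450: √(2/450) = 0.067. The gap is 0.13 SD, and it carries 0.065 SD.

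In both cases the carry-over is about one standard error of the unadjusted outcome difference. This is random error, not bias, but adjustment removes it.

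**3. What the conditional rule does to error rates**

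Null trials were simulated for a continuous outcome: 600 patients in equal arms, two-sided 5% test, 6,000 trials for each of four assumed sets of effects. Correlation with the outcome was 0.2 to 0.4 for age, 0.1 for sex and 0.3 to 0.7 for the baseline value.

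| Analysis | Type I error |
|---|---|
| Adjust for age and sex only if either differs at p < 0.05 (triggered in about 10% of trials) | 4.4% to 5.2% |
| Freely take the more favourable of the unadjusted and age/sex-adjusted results | 6.3% to 6.8% |

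With an age correlation of 0.3 and a sex correlation of 0.1, the mean standard error was 0.082 unadjusted and 0.078 with age and sex. Adding the baseline value brought it to 0.074 (r = 0.3) or 0.052 (r = 0.7). So age and sex bring a small gain, and the day-1 value brings most of what is available once r is moderate or high.

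**4. Tracheostomy**

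No size can be given, because the documents state no tracheostomy rate and no covariate effects. The point is only that the target odds ratio is not fixed in advance.

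**The case against.** The strongest reply is that covariate lists, scales and thresholds usually sit in a statistical analysis plan, which is not shown. That has force for the details. The baseline values are not named, but they are not ruled out either, and a reader who infers that baseline adjustment is excluded goes further than the text. Even so, 6.4 does not stay silent. It commits to a covariate set and to a condition for using it, and that stated rule is the weak part.

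Other stronger readings are tempting, and the documents do not support them:

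- **That outcomes drive the choice of model.** The stated trigger is balance after randomization, a baseline property. Applied mechanically, it kept type I error near 5%. The 6.3% to 6.8% needs an analyst who picks the better result, which 6.4 does not license. The missing threshold in an open-label trial leaves room for this, and no more than that can be said.
- **That both markers are analysed against their stated aim.** The phrase "longitudinal reduction in systemic C-reactive protein levels" in 2.2 concerns CRP only, as an additional end-point. No such aim is stated for PaO2/FiO2. Even for CRP, randomisation makes the difference in levels an unbiased estimate of the same contrast as the difference in change.
- **That adjustment always narrows the interval.** This holds in expectation for the linear models with prognostic covariates. In the logistic model, adjustment can raise power without narrowing the interval for the log odds ratio.
- **That the figures above cover all secondary outcomes.** They apply to CRP and PaO2/FiO2. For ventilation-free days and days of hospitalization the gain depends on unknown correlations.

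**Conclusion.** The point holds as an avoidable inefficiency and an unfixed model choice, confined to the secondary outcomes. The estimates remain valid under randomisation. The primary Fisher test, its alpha and its power are unaffected.

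For CRP and PaO2/FiO2, omitting the day-1 value costs the equivalent of 10%, 33% or 96% more patients at r = 0.3, 0.5 or 0.7. These correlations are assumptions, and the true loss depends on the true r. The loss from conditional rather than routine age and sex adjustment is smaller, about 0.082 against 0.078 in standard error under the assumed effects. For tracheostomy the fault is one of definition: whether the odds ratio is adjusted or unadjusted is settled only after the data are seen. The change is worth making because it is nearly free, not because the present rule would give wrong answers.

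**What to change.** In Protocol 6.4:

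1. Delete the condition on imbalance in both sentences where it appears.
2. Always adjust the linear models for age and sex.
3. For CRP and PaO2/FiO2 at days 3, 7 and 14, add the outcome's own day-1 value as a covariate.
4. For tracheostomy, fix one logistic model in advance, with age and sex always included.

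A log scale for CRP, type of respiratory support as a covariate, and a single repeated-measures model are options, not part of the required change. Respiratory support in every model could overload a logistic model with few events. A repeated-measures model would first need a position on values missing after death or discharge.

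The cost is a few lines of text and no new data, since 4.6 already schedules the day-1 measurements. Patients without a day-1 value need a simple rule stated in advance.
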